3.2 Exclusion Criteria

1. Non-english speaking
2. Infection(s) unrelated to HS requiring treatment with:
 - intravenous (IV) anti-infectives (antibiotics, antivirals, antifungals) within 30 days prior to Baseline or;
 - oral anti-infectives (antibiotics, antivirals, antifungals) within 14 days prior to Baseline, except as required as part of an anti-TB regimen;
3. Subject previously treated with a biologic medication but stopped due to lack of effect/sufficient effect as deemed by the investigator.
4. Any other active skin disease or condition (e.g., bacterial, fungal or viral infection) that may interfere with assessment of HS;
5. Pregnant (or considering becoming pregnant) or lactating females
Note: Nonchildbearing potential is defined as surgically sterile with a hysterectomy and/or bilateral oophorectomy OR postmenopausal (defined as amenorrhea at least 12 months before screening, confirmed by FSH levels at screening).
6. Clinically significant abnormal screening laboratory results as evaluated by the Investigator.
7. Subject does not have reliable internet access for weekly electronic surveys;
8. Subject is considered by the Study Investigator, for any reason, to be an unsuitable candidate for the study.

9. Excluded/prohibited concomitant medication and procedures include: JAK inhibitors (systemic or topical (eg, ruxolitinib, tofacitinib, baricitinib, filgotinib, lestaurtinib, and pacritinib)) within 4 weeks of Screening ; surgical, laser, or IPL intervention in area with HS lesion within 3 months of Screening, except for rescue lesional treatment; systemic corticosteroid within 4 weeks; use of topical creams, ointments, gels, and liquids except the study therapy.
10. Prolonged QT interval corrected for heart rate using Fridericia's formula (QTcF), defined as ≥ 450 msec.

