3.0 Inclusion and Exclusion Criteria

3.1 Inclusion Criteria

1. Male or female subjects age 12 years or older
 - This inclusion criteria has been updated due to the approval of the study medication for use in this age group (12 years and older) in other indications. Additionally, Humira, an approved biologic medication for HS, is also used in this population, highlighting the need for topical breakthrough treatments for those affected by HS at younger ages. Due to the open-label nature of this medication and the anticipated benefits for any children participating, the greater than minimal risk of this study design is justified.
2. Hidradenitis suppurativa, and should be Hurley Stage I or II, defined as papules, nodules, and/or abscess formation, single or multiple, with or without sinus tracts;
3. Subjects must have a diagnosis of HS for at least 3 months (90 days) prior to Baseline;
4. Active HS lesions must be present in at least one distinct anatomic area;

5. Subject must have at least 3 total inflammatory lesions at the Baseline visit;
6. Subjects who had surgery in the treatment area, should be at least 3 months status post the procedure (this applies to deroofting/marsupialization or excision, not incision & drainage)
7. Subject has a negative TB screening assessment (including a PPD test and/or T-Spot) OR for patients with treated latent TB or negative chest x-ray (CXR posterior-anterior [PA] and lateral view within prior 90 days) at Screening with documentation of treated latent tuberculosis (90 days of treatment).
8. Medications can be continued if they have been at a stable dose for the requisite duration and the dose is not increased during the study period:
 - Biologic medication (such as TNF α , IL-12/23 or IL-17 inhibitors): Up to 30% of enrolled participants will be allowed to remain on a concurrent biologic at stable dosage if treated with a stable dose and frequency for 6 months or longer;
 - Oral antibiotic must be a stable dose and frequency for 28 days or longer;
 - Hormone-based therapy (birth control pills or spironolactone) must be a stable dose and frequency for 4 months or longer;
 - Oral retinoids must be on a stable dose and frequency for 90 days or longer;
 - Other topical therapy must be discontinued 14 days prior to the Baseline visit.

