7.2 Study Procedures**7.2.1 Screening visit**

Informed consent	Laboratory screening obtained* 
 • Hepatitis B and Hepatitis C surface and core antibodies • Interferon-releasing assay for tuberculosis (or chest x-ray for those with a history of positive PPD) • Complete blood count (CBC) with differential • Hepatic panel (AST, ALT, Alk phos) • Fasting lipid panel (total, high-density, and low density cholesterol and triglycerides) • Pregnancy testing for women of child bearing potential (WOCBP)**
Inclusion/exclusion criteria reviewed	
Complete physical exam	
Clinician assessments (Lesion count, Hurley stage, HASI)	
Clinical photography of all lesions (do not include face)- kept in research files	
ECG	
Alcohol intake and recreational drug use	
Begin weekly surveys (more details below)	

*All blood will be obtained at Penn State Health outpatient laboratory.

**If subjects are postmenopausal, (defined as amenorrhea at least 12 months before screening) this will be confirmed by FSH levels drawn at the clinical site (approx. 2 teaspoons of blood)

Begin weekly surveys – These will be completed by the participants weekly through the end of Week 16 through REDCap. The weekly instruments will include patient-reported measures: NRS pain with 24-hour recall, NRS pain with 7-day recall, Hidradenitis suppurativa Quality of Life instrument (HiSQOL); medication use (assessing use of rescue medications or other potentially modifying medications or interventions).

7.2.2 Week 0, Baseline visit (28 ±5 days)- Can be combined with Screening Visit

Subjects will have a combined Screening/Baseline visit if all Inclusion/Exclusion criteria is met at the Screening visit.

Complete physical exam	Patient reported measures- collected electronically
------------------------	---

Clinician reported measures collected	WOCBP only- urine sample for pregnancy
Clinical photography	Dispense and start treatment with topical ruxolitinib 1.5% cream. Study coordinator will provide instructions for twice daily application.
Target lesion evaluated	Tissue sample collected (details below)

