7.4.6.5 Prior and Concomitant Therapy

All concomitant medications and treatments (including over-the-counter or prescription medicines, vitamins, vaccines, and/or herbal supplements) will be recorded on electronic study forms in REDCap. Any addition, deletion, or change in the dose of these medications will also be recorded. Concomitant treatments/procedures that are required to manage a participant's medical condition during the study will also be recorded in the REDCap study forms.

Any prior medication received up to 28 days before the first dose of study treatment and 30 days after the last dose of

study treatment will be recorded in the REDCap study forms. A detailed history of prior medications use related to HS in the year before screening will be also be collected, as well as response to each treatment and reason for discontinuation.

Excluded/prohibited concomitant medication and procedures include: JAK inhibitors (systemic or topical (eg, ruxolitinib, tofacitinib, baricitinib, filgotinib, lestaurtinib, and pacritinib)) in the 4 weeks prior to screening; surgical, laser, or IPL intervention in area with HS lesion in prior 3 months and except for rescue lesional treatment (see below); topical use of creams, ointments, gels, and liquids except the study therapy.

All medications used by the patient will be reconciled at entry into the study and through electronic surveys or in-person study visits throughout the entire study duration.

If a participant experiences significant pain after baseline, one of the following analgesic regimens may be initiated at any time: Ibuprofen (at a dose of up to 800 mg orally every 6 hours) not to exceed 3200 mg/24 hours OR acetaminophen not to exceed 4 g/24 hours. Participants can use one of the permitted antiseptic therapies. Permitted antiseptic washes are limited to one of the following: chlorhexidine gluconate, triclosan, benzoyl peroxide, or diluted bleach in bathwater. Participants can use wound care dressings on HS wounds. Options are limited to alginates, hydrocolloids, and hydrogels.

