8.2 Sample size determination

Based on the placebo and effect responses for adalimumab in the PIONEER trials (Kimball, 2016) for moderate-to-severe HS, the HiSCR response rate in the placebo group was approximately 27% (26.0% and 27.6%) and HiSCR rates of 42-59% for adalimumab. In mild-to-moderate and moderate-only HS treated with apremilast, the placebo HiSCR rate was 0% and in the response rate in the intervention groups was 53-55% (Kerdel 2019, Vossen 2019).

With a sample size of at least 18 participants, we will have sufficient power to determine if the HiSCR response rate for topical ruxolitinib 1.5% cream is 55% and significantly different from a 20% (or lower) placebo response rate with a power of 80% and risk of type I error of 5%. Typically, in a Simon's two-stage design, 11 patients would be accrued in the first stage and 7 additional in the second phase; however, we will accrue all in one cohort of at least 18 completed participants. The null hypothesis will be rejected if 5 or more responses are observed in 18 completed participants.

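### The two prohibited-therapy lists disagree, the text is unclear on other systemic HS drugs, and no rule says how HiSCR is scored when a completer starts or increases one

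*Combined protocol and SAP*

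**What the plan says.** **Prohibited therapy.** Section 3.2 item 9 opens "Excluded/prohibited concomitant medication and procedures include: JAK inhibitors" and goes on to procedures, "systemic corticosteroid within 4 weeks" and topicals. Section 7.4.6.5 opens its list the same way, but passes from procedures straight to topicals: "except for rescue lesional treatment (see below); topical use of creams, ointments, gels, and liquids except the study therapy". Systemic corticosteroid is missing there, and the JAK inhibitor limit is given only as "in the 4 weeks prior to screening".

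**Background therapy.** Section 3.1 item 8 says "Medications can be continued if they have been at a stable dose for the requisite duration and the dose is not increased" during the study. It then gives stability periods for four systemic classes: biologics, oral antibiotics, hormonal therapy and oral retinoids.

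**New therapy on study.** Section 7.4.6.5 bars new systemic and topical therapies, antibiotics included, after incision and drainage. Elsewhere in that section, additions and dose changes are to be recorded. The risk table in Section 10.0 allows a short antibiotic course for superinfection. Section 3.3.1 names receipt of disallowed treatment as one possible reason for withdrawal.

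**Outcome and analysis.** Section 1.2 defines HiSCR by abscess, nodule and draining fistula counts. Sections 1.2 and 8.3 analyse completers, and Section 8.3 adds last observation carried forward for missing data. Neither mentions other systemic therapy.

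**The concern.** The trial has one open-label arm, so no control group absorbs the effect of a co-treatment. Any fall in lesion count is credited to the cream. The plan's own sample-size section shows that another systemic drug could produce the effect being sought: for apremilast in mild-to-moderate or moderate HS, it reports that "the response rate in the intervention groups was 53-55"%, against a target of 55% for ruxolitinib.

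Two things are at stake. First, a site cannot tell from the text whether some on-study systemic treatments are deviations. Second, even where such a treatment is clearly a deviation, nothing says whether that participant is a responder, a non-responder or excluded. Without a rule, the choice would be made with open-label results in view.

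**Working it through.** **Passages side by side**

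| Question | What the text gives |
|---|---|
| Systemic corticosteroid on study | Section 3.2: listed as prohibited, 4 weeks not anchored. Section 7.4.6.5: not listed |
| Other systemic HS drug at entry | Section 3.1 item 8 names four classes and does not say what happens to the rest |
| New systemic drug on study | Barred after incision and drainage (7.4.6.5); short antibiotic course allowed for superinfection (10.0); otherwise additions are recorded |
| Consequence of disallowed treatment | Withdrawal possible, not required (3.3.1) |
| Consequence for HiSCR | None stated (1.2, 8.3) |

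So a participant who adds a systemic HS drug, stays to Week 16 and meets the counts is a responder. One who is withdrawn for the same reason leaves the completer set. The classification depends on what the site does.

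**The plan's own figure.** Section 8.2 rejects a 20% rate if at least 5 of 18 respond, and claims 5% type I error and 80% power at 55%. Exact binomial tails:

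- cut-off 5: P(Bin(18, 0.20) ≥ 5) = 0.284; P(Bin(18, 0.55) ≥ 5) = 0.995
- cut-off 7: 0.051 and 0.946
- cut-off 8: 0.016 and 0.872

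The stated figures do not reproduce at 5. That is a separate defect. To keep it out of this point, cut-off 8 is used as the main illustration, because it is the smallest that holds 5% exactly.

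**Illustration of the bias.** Inputs: n = 18, background p = 0.20 (Section 8.2), and q = 0.54, the midpoint of the 53-55% in Section 8.2. The number k of completers on a newly started drug is an assumption. Participants are taken as independent and the cream as inactive.

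Expected rate = [k × 0.54 + (18 − k) × 0.20] / 18

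P(at least r responders) = Σ over y from 0 to k of P(Bin(k, 0.54) = y) × P(Bin(18 − k, 0.20) ≥ r − y)

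For k = 2 and r = 8: 0.2116 × 0.0070 + 0.4968 × 0.0267 + 0.2916 × 0.0817 = 0.0015 + 0.0132 + 0.0238 = 0.0385.

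| k | Expected rate | r = 8 | r = 5 (as stated) |
|---|---|---|---|
| 0 | 20.0% | 1.6% | 28% |
| 2 | 23.8% | 3.9% | 43% |
| 3 | 25.7% | 5.7% | 51% |
| 4 | 27.6% | 8.2% | 59% |

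**Effect of scoring those k as non-responders, cut-off 8.** False-positive risk is P(Bin(18 − k, 0.20) ≥ 8) and power is P(Bin(18 − k, 0.55) ≥ 8).

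| k | False-positive risk | Power at 55% |
|---|---|---|
| 0 | 1.6% | 0.87 |
| 2 | 0.7% | 0.74 |
| 3 | 0.4% | 0.65 |

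**The case against.** A reader might infer that the plan lets a participant start systemic steroid on study without breaking any rule. The documents do not support that. Section 3.2 lists systemic corticosteroid under concomitant medication that is prohibited, and unlike the JAK and procedure items it is not tied to Screening. Both lists also make exceptions for rescue treatment and the study cream, which only make sense on study. The two sections conflict, and a conflict is not permission.

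A reader might also infer that someone may enter on recently started apremilast. Section 3.1 item 8 can fairly be read as a closed list of what may continue, the prohibited lists are introduced as inclusive rather than exhaustive, and Section 3.2 item 8 lets the investigator exclude any unsuitable candidate. The text is ambiguous, not permissive. Nor would the 54% rate fit a participant on established apremilast, whose baseline count already reflects the drug.

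Finally, the documents give no frequency for such starts, and the 28% starting point at cut-off 5 comes wholly from the cut-off. The 43% to 59% figures therefore cannot be read as the effect of this gap.

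All of this stands, and it narrows the point. It does not supply the missing scoring rule: discretion at entry does not govern a later start, and calling something a deviation does not say how it is analysed.

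**Conclusion.** The concern holds in limited form. The steroid entry differs between Sections 3.2 and 7.4.6.5. The position of other systemic HS drugs is silent or ambiguous across Sections 3.1, 3.2, 3.3.1, 7.4.6.5 and 10.0. No rule stops a completer who starts or increases such a drug from counting as a HiSCR responder. The bias in the single-arm proportion is upwards.

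Its size cannot be known from the documents. If 2 to 4 of 18 were affected, the expected rate under an inactive cream would rise by about 4 to 8 percentage points (23.8% to 27.6%, against 20%), and the false-positive risk at cut-off 8 from 1.6% to between 3.9% and 8.2%. This rests on the assumed k, on the 54% rate applying to a drug newly started on study, and on independence. With no such starts there is no bias, but the contradiction between the lists remains.

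**What to change.** 1. **Reconcile the passages.** Bring Section 3.1 item 8, Section 3.2 item 9, Section 3.3.1, Section 7.4.6.5 (both the therapy list and the paragraph on interventions) and the Section 10.0 risk table into agreement, and state the period each restriction covers. What is allowed or barred is for the sponsor to decide.

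2. **Add a scoring rule to Section 8.3.** A participant who starts, or increases the dose of, a systemic drug for HS between Baseline and Week 16 is scored as a HiSCR non-responder in the primary analysis. State how the antibiotic course in Section 10.0 is classified, and whether the rule also covers participants withdrawn for this reason, whom a completer set would otherwise drop. Add a sensitivity analysis that scores HiSCR as observed.

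The rule concerns the outcome only and leaves care unchanged. It needs no new data, because the weekly survey in Section 7.2.1 already records "medication use (assessing use of rescue medications or other potentially modifying medications or interventions".

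The cost is a few sentences, a lower reported response rate, and power if such starts are common: at cut-off 8, power at 55% falls from 0.87 to 0.74 if 2 of 18 are affected.

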3.3 Early Withdrawal of Subjects

3.3.1 Criteria for removal from study

Some possible reasons for an early withdraw might be subjects require or receive treatment that is not allowed in this study, subject becomes pregnant, subject experiences side effects from the study treatments that they find unacceptable, HS worsens according to the study doctor's assessment, or subject does not follow instructions.

3.3.2 Follow-up for withdrawn subjects

If a subject withdraws completely from the research study, no further information will be collected and his/her participation will end. All attempts will be made to conduct the last study visit and perform all early termination assessments.

4.0 Recruitment Methods

4.1 Identification of subjects

Subjects will be recruited through STUDYfinder. [name] will be recruiting from her dermatology clinic. She, and other dermatology providers, will identify participants during their regularly scheduled visits (interactions during a clinic visit). Additionally, an established recruitment database of HS patients may be used.

4.2 Recruitment process

4.2.1 How potential subjects will be recruited.

Subjects will call the study line at the research site. The coordinator will call and if the subject decides to schedule an appointment, the coordinator will schedule a screening visit. The site will utilize a screening form for all potential subjects. Subjects who are identified in clinic will call the research office or stop in after their regular scheduled appointment for their screening visit at another time.

4.2.2 Where potential subjects will be recruited.

[name] will be recruiting from her dermatology clinic and online resource STUDYFinder. We will also be utilizing our HS database and contacting previous

dermatology research participants who agreed for the study team to be contacted for upcoming trials.

4.2.3 When potential subjects will be recruited.

Potential subjects will be recruited during their regular scheduled HS Dermatology clinic visit by the study coordinator.

4.2.4 Describe the eligibility screening process and indicate whether the screening process will occur before or after obtaining informed consent. Screening begins when the investigator obtains information about or from a prospective participant in order to determine their eligibility. In some studies, these procedures may not take place unless HIPAA Authorization is obtained OR a waiver of HIPAA Authorization when applicable for the screening procedures is approved by the IRB. [For FDA regulated studies, consent for any screening activities would need to be obtained prior to screening unless specifically waived by the IRB.]

Subjects will call the site to be screened. If the subject decides to schedule an appointment the coordinator schedules a screening visit. If the subject declines, the telephone screening is discarded.

5.0 Consent Process and Documentation

5.1 Consent Process:

Check all applicable boxes below:

- ☒ Informed consent will be sought and documented with a written consent form
[Complete Sections 5.2 and 5.6]
- ☐ Implied or verbal consent will be obtained – subjects will not sign a consent form
(waiver of written documentation of consent) [Complete Sections 5.2, 5.3 and 5.6]
- ☐ Informed consent will be sought but some of the elements of informed consent
will be omitted or altered (e.g., deception). [Complete section 5.2, 5.4 and 5.6]
- ☐ Informed consent will not be obtained – request to completely waive the informed
consent requirement. [Complete Section 5.5]

5.2 Obtaining Informed Consent

5.2.1 Timing and Location of Consent

The consent will take place in the Dermatology Research Office, UPC II-RM 2010 in a private room by a research coordinator

5.2.2 Coercion or Undue Influence during Consent

Subjects will have ample time to read and ask questions about the study. Their involvement in the study will not affect their treatment if they are currently patients of the dermatology clinic.

5.3 Waiver of Written Documentation of Consent

5.3.1 Indicate which of the following conditions applies to this research:

☐ The research presents no more than minimal risk of harm to subjects and involves no procedures for which written consent is normally required outside of the research context.

OR

☐ The only record linking the subject and the research would be the consent document and the principal risk would be potential harm resulting from a breach of confidentiality. Each subject will be asked whether the subject wants documentation linking the subject with the research, and the subject's wishes will govern. *(Note: This condition is not applicable for FDA-regulated research. If this category is chosen, include copies of a consent form and /or parental permission form for participants who want written documentation linking them to the research.)*

OR

☐ If the subjects or legally authorized representatives are members of a distinct cultural group or community in which signing forms is not the norm, that the research presents no more than minimal risk of harm to subjects and provided there is an appropriate alternative mechanism for documenting that informed consent was obtained. *(Note: This condition is not applicable for FDA-regulated research.)*

Describe the alternative mechanism for documenting that informed consent was obtained:

Each consented participant will have ICF process documented on their source.

5.3.2 Indicate what materials, if any, will be used to inform potential subjects about the research (e.g., a letter accompanying a questionnaire, verbal script, implied consent form, or summary explanation of the research)

Coordinator will complete a screening form for each potential participant

5.4 Informed consent will be sought but some of the elements of informed consent will be omitted or altered (e.g., deception).

5.4.1 Indicate the elements of informed consent to be omitted or altered

NA

5.4.2 Indicate why the research could not practicably be carried out without the omission or alteration of consent elements

NA

5.4.3 Describe why the research involves no more than minimal risk to subjects.

NA

5.4.4 Describe why the alteration/omission will not adversely affect the rights and welfare of subjects.

NA

5.4.5 If the research involves using identifiable private information or identifiable biospecimens, describe why the research could not be practicably be carried out without using such information or biospecimens in an identifiable format.

NA

